## 17.2 Operational Committee

The OC is composed of Centre Leads selected by the TSC from investigators in each centre with appropriate clinical trial experience. The OC will be co-chaired by representatives from the MRC Epidemiology Unit and the DTU. The primary role of the OC is to serve as the interface between the TSC and the study sites. Committee members will be instrumental in serving as ambassadors of the study to encourage recruitment as well as ensure study compliance by working with study personnel and mediating in centre-specific issues. The committee will provide a means of transmitting any identified needs, concerns, or suggestions from the sites to the TSC and assist in disseminating clinical or operational information to the sites. The functions and operating procedures of the OC are delineated in a charter. Specific functions of the OC will include the following:

1. All members will serve as advocates for the study.

2. Centre Leads will:

• Communicate with investigators in their respective centres to review centrespecific progress reports, including but not limited to recruitment/retention of participants, event reporting and data collection, and communication between sites and usual care providers.

• Communicate with investigators in their respective centres to review and attempt to resolve any operational issues raised by their centre

3. Committee Co-Chairs will:

• Compile centre-specific performance metrics for presentation to the TSC

• Liaise with Centre Leads, academic coordinating centres (MRC Epidemiology Unit and DTU project teams), and sponsor to implement study policies.

#### 17.3 Independent Data Monitoring Committee

The IDMC will be composed of five senior academic individuals, including the IDMC Chair. There will be at least one member with expertise for each of cardiology, endocrinology, and oncology, and an Independent Statistician (not affiliated to the MRC

Epidemiology Unit, DTU, or the Sponsor) and a Sponsor representative. All of these individuals will have long-standing experience in the operational, medical, and biostatistical aspects of clinical trials. The MRC Epidemiology Unit senior statistician assigned to GLINT will oversee the provision of interim masked data sets for use by the IDMC and the MRC Epidemiology / DTU study coordinating centres. DTU will transfer pre-agreed masked datasets to the Independent Statistician who will then prepare unmasked confidential reports for the IDMC, using treatment codes provided in advance by the Informatics Group at the DTU. During the Open Session of the IDMC meetings, representatives of the TSC may present updates on the study status or the safety profile of metformin, but will not be privy to discussions of the unmasked data conducted during the Closed Sessions and will not vote. Proceedings and minutes of the Closed Session will be held in strict confidence and will not be shared outside the IDMC while the study is ongoing.

During the feasibility phase, the IDMC will meet after 250 participants have been recruited, and will report to the TSC before the full study commences. Thereafter, the IDMC will meet every six months during the full study.

The IDMC will be responsible for the interests of the participants and, to this end, will undertake regular reviews of the safety data (including SAEs). The IDMC will have access to an agreed subset of the study data as listed in the IDMC charter (updated as necessary during the study) in an unblinded fashion throughout the study duration. In addition, the IDMC will evaluate interim analyses of the data every six months, or on an ad hoc basis if needed, to determine if it believes either the study should be terminated early because the metformin arm (with respect to the placebo arm) demonstrates (a) clear inferiority, i.e., it is not in participant's best interest to continue taking blinded therapy; or (b) clear superiority, i.e., it is not in participant's best interest to continue taking blinded placebo. If the IDMC finds it necessary to recommend actions regarding interruption of the study or changes to the protocol based on medical rationale that would make it unethical to continue the study in its present form, those recommendations will be forwarded to the TSC. The details of the IDMC's functions and the early stopping rules will be delineated in a separate IDMC charter.

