#### 9.5 Emergency Unblinding

The study phone line can be used to unblind participants to the randomised treatment assignment only if deemed clinically essential by those with responsibility for providing health care to the participant and the duty study clinician, that is to say in a situation in which the responsible clinician considers that the treatment received in the study needs to be identified in order to appropriately manage the participant's presenting condition. Drug identification information is to be unmasked ONLY if necessary for the welfare of the participant and will only be undertaken by those with appropriate delegated authority. All participants will be provided with a study contact card to present to any clinician that may treat them. The study card will have details of the 24 hour phone line (details of which will also be included on other key documents such as the Participant Information Leaflet). The 24 hour telephone number will be available during office hours, and by a study clinician outside of office hours, who will be able to unblind a participant if required. It is the responsibility of the Investigator or the team member

who completes the unblinding to promptly document and explain any unblinding to the Sponsor as per SOP.

The unblinding system is accessed electronically via the trial management system and can be accessed 24 hours a day. Any occurrence of an unblinding event will be recorded in the web-based electronic trial management system, which records the time, date and operator as well as the reason for unblinding, but not the allocated treatment. The study Sponsor will be informed of any unblinding occurrences. The data required to break the code are, however, stored in the separate encrypted Medication & Codebreak Database and only accessible to the site investigators or the 24 hour phone line team members.

The GLINT team at the MRC Epidemiology Unit, University of Cambridge will operate the phone line. The phone line will also be available to answer urgent clinical questions from sites concerning enrolled participants (adverse events, unblinding etc.) as well as questions to determine whether a particular participant qualifies for enrolment. Each site will have site-specific phone lines for participant queries to be manned during normal office hours.

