# **17 Study Committees**

#### 17.1 Trial Steering Committee

The GLINT Trial Steering Committee (TSC) will have responsibility for the oversight of the study (Figure 1). The TSC will consist of nine individuals, comprising three senior independent academic representatives who are experts in their field (one of whom will chair the committee), four GLINT PIs, one lay representative and a Sponsor representative. A TSC charter will delineate operating procedures. The TSC is the main decision-making body for GLINT and is charged with the overall scientific, professional, and operational conduct of the study. The primary functions of the TSC are to:

1. Review and approve the study protocol and all protocol amendments.

2. Supervise the conduct of the study in accordance with its responsibilities described in the study protocol.

- 3. Review and approve the Statistical Analysis Plan.
- 4. Oversee all study subcommittees, including but not limited to:
  - Clinical endpoint committee
  - Data monitoring and ethics committee

• Operational committee

5. Review and consider recommendations from the IDMC

6. The TSC will determine the time to terminate the study, based on recommendations from the IDMC and other available information. The TSC may also find it necessary to terminate the study under certain circumstances, including but not limited to the following reasons:

• Animal, human or toxicological test results, in the reasonable determination of the TSC, support termination of the study

• Ethical or participant safety issues occur that the TSC feels support termination of the study

• Extraordinary scientific, regulatory or other events that negatively impact the rationale for the study such that the TSC agrees it is appropriate to terminate the study 7. Review all sub-study requests and approve where appropriate.

8. Consider, authorise as appropriate and prioritise requests for access to GLINT study data and genetic samples for academic or other collaborations. After the TSC disbands, the MRC Epidemiology Unit, DTU and the sponsor will assume this responsibility.

9. Approve the communication strategy on how to best communicate information about the progress of the study.

10. Ensure accurate, uniform, timely, and high quality reporting of the full study and all approved sub-studies.

11. All members of the TSC will have access, in confidence to the draft manuscript describing the primary results paper.

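### Section 17.3 seats a Sponsor representative on the Independent Data Monitoring Committee and does not bar that person from unmasked comparative data or from voting

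*Protocol*

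**What the plan says.** Section 17.3 sets the size of the committee: "The IDMC will be composed of five senior academic individuals, including the IDMC Chair". It then lists who sits on it: "There will be at least one member with expertise for each of cardiology, endocrinology, and oncology, and an Independent Statistician (not affiliated to the MRC", and the sentence closes with "Epidemiology Unit, DTU, or the Sponsor) and a Sponsor representative". Non-affiliation with the sponsor is thus required of the statistician alone, and the sponsor's own representative is named in the same list.

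On data flow, the independent statistician is to "prepare unmasked confidential reports for the IDMC, using treatment codes provided in advance by the Informatics Group at the DTU". The committee has access to an agreed subset of the data "in an unblinded fashion throughout the study duration", and "the IDMC will evaluate interim analyses of the data every six months, or on an ad hoc basis if needed", looking for clear inferiority or superiority of metformin. Section 15.4 confirms that its review covers the main outcomes as well as safety.

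Section 17.3 keeps TSC representatives out of the unmasked discussion and denies them a vote. It also keeps Closed Session proceedings inside the IDMC while the study runs. Neither rule mentions the Sponsor representative.

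Section 17.1 gives the sponsor a seat on the TSC too: "one lay representative and a Sponsor representative".

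**The concern.** A monitoring committee is called independent so that people who can still change the trial do not know the emerging treatment effect. Here a party that can change the trial has a seat inside the committee. The University of Cambridge is a co-sponsor, and its MRC Epidemiology Unit runs the trial jointly with the Oxford unit (Section 7). Section 18.4 requires sponsor agreement to every amendment. Through the TSC the sponsor also has a voice in approving amendments and the SAP and in deciding when to terminate (Section 17.1). Under Section 15.6 the SAP need only be published before unblinding, so it could be settled after several comparative reviews have taken place.

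If the representative sees by-arm results, decisions on amendments, the SAP and termination could be made, or be suspected of having been made, with knowledge of them. That knowledge cannot be withdrawn later, and the claim of independent monitoring would be open to challenge.

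**Working it through.** This is mainly a reading of the text, with two small counts.

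**1. Is the representative a member?** The minimum seats listed in 17.3 are cardiology 1 + endocrinology 1 + oncology 1 + statistician 1 + Sponsor representative 1 = 5, which equals the stated size. The sentence that follows describes the experience of all the individuals just listed. Membership is therefore the natural reading. The count does not prove it, because 17.3 asks for at least one member per specialty. For example, 2 cardiologists + 1 endocrinologist + 1 oncologist + 1 statistician = 5 without the sponsor.

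**2. What do members receive?** The reports are unmasked and addressed to the IDMC without distinction between members. The reviews ask whether metformin is clearly inferior or superior, and 15.4 includes main outcomes. The agreed subset must therefore contain comparative outcome data.

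**3. Who is excluded?**

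| Role in 17.3 | Must be unaffiliated to the sponsor | Kept from unmasked discussion | Denied a vote |
|---|---|---|---|
| Independent statistician | yes | no | not stated |
| TSC representatives | not stated | yes | yes |
| Sponsor representative on the IDMC | no | not stated | not stated |

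The Protocol has the right safeguard and applies it to the TSC, but not to the sponsor seat.

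**4. How many reviews?** The interval is six months, so 2 per year (17.3). The anticipated duration of the full study is 5 to 7 years (Section 5, synopsis).

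- Lower: 5 × 2 = 10
- Upper: 7 × 2 = 14

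This leaves out the feasibility-phase meeting after 250 participants and any ad hoc meetings. It counts opportunities for access and does not measure bias.

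**5. Are the two sponsor seats separate?** The TSC has 3 independent academics + 4 PIs + 1 lay member + 1 Sponsor representative = 9. Nothing in 17.1 or 17.3 requires the sponsor's representatives on the two committees to be different people.

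The target of 1,046 events, the power and the significance level do not enter this point.

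**The case against.** The strongest reply is that access is inferred. No sentence says that this person attends Closed Sessions, reads the unmasked reports or votes. Section 17.3 leaves the details of the committee's functions to a charter that is not shown and that may confine the role to Open Sessions. This stands as a limit on what can be claimed: the representative is not barred from the data, which is less than saying that the representative sees them. It does not remove the point, because the Protocol itself fixes the composition and the recipients of the reports, and a restrictive charter would have to cut across that text.

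Closed Session confidentiality is a real safeguard, but a partial one. It stops information leaving the IDMC, and this person is inside it. The sponsor is an NHS trust and a university, which may lessen financial conflict, but one of the two sponsors houses a unit that runs the trial.

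The routes to harm are also narrower than they might seem. Close-out is tied to 1,046 adjudicated events unless the TSC terminates (8.4), and the SAP is reviewed by an outside biostatistics group as well as the TSC (15.6).

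A reader might infer three further things that the Protocol does not support:

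- **That the seat breaches 9.3 or 9.5.** Section 9.3 restricts participant-level allocation codes. Section 9.5, where the log holds "the reason for unblinding, but not the allocated treatment", concerns emergency unblinding of single participants. Neither governs aggregate IDMC reports, which 17.3 expressly plans. Section 9.4 covers participants and trial personnel, and no sentence states that the sponsor is masked.
- **That adjudication is compromised.** Section 17.4 makes the Clinical Events Committee independent and blinded, with pre-specified criteria.
- **That nobody in the sponsor or coordinating units may see by-arm data before lock.** Section 15.2 plans a feasibility analysis by randomised group to inform the decision to proceed, so such a rule would create a new contradiction.

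**Conclusion.** The point holds as a governance defect in the text of 17.3. The section places a Sponsor representative on a committee titled Independent, sends that committee unmasked comparative outcome data, and exempts only TSC representatives from seeing it. Followed as written, nothing keeps a party with authority over amendments, and a seat on the body that approves the SAP and decides termination, from by-arm results at about 10 to 14 reviews.

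This rests on two assumptions: that being named in the composition sentence means membership, which is the natural but not the only reading, and that the charter does not already restrict the role. The count also assumes a full study of 5 to 7 years with meetings on schedule. The conflict with the committee's title, and the contrast with the treatment of TSC representatives, need neither assumption. The size of any resulting bias cannot be computed from the Protocol.

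**What to change.** In Section 17.3 and the IDMC charter, do one of the following:

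- remove the Sponsor representative from IDMC membership; or
- state that this person attends Open Sessions only, receives no unmasked reports and does not vote, matching the existing rule for TSC representatives.

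Then correct the member count, so that the five members are reached without the sponsor seat or the stated number is changed. With either option, it no longer matters whether the sponsor's representatives on the TSC and at the IDMC are the same person.

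Leave the by-group feasibility analysis in 15.2 as it is. The cost is a few sentences in the Protocol and charter and possibly one replacement independent member. The change should be in place before the IDMC's first unmasked review.

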# 17.4 Clinical Events Committee (CEC)

The events which constitute the principal endpoints of this study will be adjudicated by an independent CEC, coordinated through the MRC Epidemiology Unit, which will include at least two clinically qualified members. The specific endpoints to be adjudicated include: CV mortality, nonfatal myocardial infarction, nonfatal stroke, allcause mortality, hospital admission for congestive heart failure, hospitalisation for unstable angina; coronary, cerebrovascular or peripheral revascularization. Clinicians will review study data and efficacy endpoints using pre-specified criteria and definitions. The CEC will be blinded to the assigned study drug. Sites will provide clinical information via the eCRF and also provide supplemental information from medical records, when needed. The CEC operations and endpoint criteria will be described in a separate charter.

Figure 1: GLINT governance structure

#### 18 Ethical & Regulatory considerations

The conduct of the study will be monitored by a steering committee including independent members and a lay member. See also Section 17 above, which outlines IDMC responsibilities during the full study.

#### 18.1 Consent

The Informed Consent form must be approved by the REC and must be in compliance with GCP, local regulatory requirements and legal requirements. The investigator must ensure that each study participant, or his/her legally acceptable representative, is fully informed about the nature and objectives of the study and possible risks associated with their participation. The informed consent form used for this study and any change made during the course of this study, must be prospectively approved by the REC. The investigator will retain the original of each participants signed informed consent form.

For the purposes of this study we will only include participants with a good written and verbal understanding of the English language.

We will ask all potential participants to provide written informed consent in order to be recruited to the study, and to allow access to information contained in medical records for responsible members of the GLINT team. In addition, we will request informed consent to monitor participants' vital status (dead/alive) and collect information on potential endpoints using data from ONS and the Information Services Division of the Scottish Government, the National Cancer Registry, HES, from their GP, the NHS tracking system, and share contact details with authorised third parties for the dispatch of study medication.

The participant must personally sign and date the latest approved version of the informed consent form before any study specific procedures are performed.

Written versions of the participant information and informed consent will be presented to the participants detailing no less than: the exact nature of the study; the implications and constraints of the protocol; the known side effects and any risks involved in taking part. The details of the study will verbally communicated to the participants during the informed consent procedure by a trained member of staff. It will be clearly stated that the participant is free to withdraw from the study at any time for any reason without prejudice to future care, and with no obligation to give the reason for withdrawal.

The participant will be sent an information sheet and consent form at least one week in advance of their recruitment visit to consider the study information. They will be given an opportunity to question the Investigator, their GP or other independent parties to decide whether they will participate in the study. The staff member taking consent will ensure that the participant has read and understood the information sheet prior to taking consent. We will not include people with an impaired ability to give consent to the study.

Written informed consent will be obtained by means of participant dated signature and dated signature of the person who presented and obtained the informed consent. The person who obtained the consent must be suitably qualified and experienced, and have been authorised to do so by the Chief/Principal Investigator. A copy of the signed informed consent will be given to the participants. The original signed form will be retained at the study site.

Consent will also be sought from study participants to store whole blood samples for future DNA analyses and a serum sample for biomarker analyses. All samples will be stored by the MRC Epidemiology Unit, University of Cambridge.

Any new information which becomes available, which might affect the participant's willingness to continue participating in the study will be communicated to the participant as soon as possible by the required means (i.e. phone, email or post) details may also be communicated on the study website.

#### 18.2 Ethical committee review

The protocol, informed consent form, participant information leaflet and any proposed advertising material will be submitted to an appropriate Research Ethics Committee (REC), regulatory authorities (MHRA), and host institution(s) for written approval.

Before the start of the study or implementation of any amendment we will obtain approval of the study protocol, protocol amendments, informed consent forms and other relevant documents e.g. advertisements and GP information letters if applicable from the REC. All correspondence with the REC will be retained in the Trial Master File/Investigator Site File.

Annual reports will be submitted to the REC in accordance with national requirements. It is the Chief Investigators responsibility to produce the annual reports as required.

#### 18.3 Regulatory Compliance

The study will not commence until a Clinical Trial Authorisation (CTA) is obtained from the MHRA. The protocol and study conduct will comply with the Medicines for Human Use (Clinical Trials) Regulations 2004 and any relevant amendments.

Development Safety Update Reports (DSURs) will be submitted to the MHRA in accordance with national requirements. It is the Chief Investigators responsibility to produce the annual reports as required.

#### 18.4 Protocol Amendments

Protocol amendments must be reviewed and agreement received from the Sponsor for all proposed amendments prior to submission to the REC and/or MHRA.

The only circumstance in which an amendment may be initiated prior to REC and/or MHRA approval is where the change is necessary to eliminate apparent, immediate risks to the participants (Urgent Safety Measures). In this case, accrual of new participants will be halted until the REC and/or MHRA approval has been obtained. Participants would be notified in writing in the event of an urgent safety measure.

